3 PRIMARY AND SECONDARY VARIABLES

3.1 Efficacy variables

3.1.1 Objective response rate (ORR)

ORR is defined as the percentage of patients with a confirmed investigator-assessed response of complete response (CR) or partial response (PR) from the date of re-initiation of treatment with durvalumab monotherapy. ORR will be assessed in the response evaluable analysis set (patients who are retreated with durvalumab in Cohort 2).

A confirmed response of CR/PR means that a response of CR/PR is recorded at one visit and confirmed by repeat imaging not less than 4 weeks after the visit when the response was first observed with no evidence of progression between the initial and CR/PR confirmation visit. Data obtained up until progression, or last evaluable assessment in the absence of progression, will be included in the assessment of ORR. Patients who discontinue treatment without progression, receive a subsequent anticancer therapy (note that for this analysis radiotherapy is not considered a subsequent anticancer therapy) and then respond will not be included as responders in the ORR (i.e., both visits contributing to a response must be prior to subsequent therapy for the patient to be considered as a responder).

In the case where a patient has two non-consecutive visit responses of PR, then, as long as the time between the 2 visits of PR is greater than 4 weeks and there is no PD between the PR visits, the patient will be defined as a responder. Similarly, if a patient has visit responses of CR- Not evaluable (NE), CR, then, as long as the time between the 2 visits of CR is greater than 4 weeks, then a best response of CR will be assigned.

CR and PR can be assessed using the following Electronic Case Report Form (eCRF) modules:

- **Overall Exam Assessment (OVERALL):**
 - Overall Assessment of Target and Non-Target Lesions**
 - Assess Target Lesions as a Whole (CR; PR; PD; Stable Disease [SD]/ Not Evaluable)
 - Assess Non-Target Lesions as a Whole (CR/PD/ Non-CR/Non-PD; Not Evaluable)
 - Overall Tumor Response Assessment (CR; PR; PD; SD; NED); Not Evaluable
 - Latest Scan Date for the Timepoint
 - Progression Scan Date

- **Tumor Evaluation: New Lesions and Investigator Assessment of Response (RECIST2)**

Overall visit response

- RECIST response (CR; PR; PD; SD(Non-CR/Non-PD); Not evaluable)
- Investigator's opinion agrees with RECIST response (yes/no)
- Investigator's opinion of patient status (Responding; Stable; Progressing)

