6.4 Concomitant therapy

The Investigator must be informed as soon as possible about any medication taken from the time of enrollment until the end of the durvalumab treatment, including the 90-day follow-up period following the last dose of study drug. This applies only for patients receiving durvalumab through 90 days after the last dose, and does not apply to patients from Cohort 2 who are not retreated and patients in Cohort 3. No restrictions apply to patients off treatment who are over 90 days from their last dose of durvalumab.

Any medication or vaccine including over-the-counter or prescription medicines, vitamins, and/or herbal supplements that the patient is receiving at the time of enrollment or receives during the study must be recorded along with:

- Reason for use
- Dates of administration including start and end dates
- Dosage information including dose, unit, and frequency

Patients must be instructed not to take any medications, including over-the-counter products, without first consulting with the Investigator.

Restricted, prohibited, and permitted concomitant medications are described in the following tables. Refer also to the Dosing Modification and Toxicity Management Guidelines (see Annex 1).

Table 7 Prohibited concomitant medications

Prohibited medications/class of drug:	Usage:
Cohort 1 and retreated patients in Cohort 2, only	
Any investigational anticancer therapy other than those under investigation in this study	Should not be given concomitantly while the patient is on study treatment
Monoclonal antibodies against CTLA-4, PD-1, or PD-L1 other than those under investigation in this study	Should not be given concomitantly while the patient is on study treatment
Any concurrent chemotherapy, radiotherapy, immunotherapy, or biologic or hormonal therapy for cancer treatment other than those under investigation in this study	Should not be given concomitantly while the patient is on study treatment. (Concurrent use of hormones for non-cancer-related conditions [eg, insulin for diabetes and hormone replacement therapy] is acceptable. Local treatment of isolated lesions, excluding target lesions, for palliative intent is acceptable [eg, by local surgery or radiotherapy].)

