9.3.3.3 Objective response rate

ORR is defined as the number (%) of patients with a confirmed response of CR or PR. Data obtained up until progression, or the last evaluable assessment in the absence of progression, will be included in the assessment of ORR. Patients who go off treatment without progression, receive a subsequent therapy, and then respond will not be included as responders in the ORR.

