3.1.2 Duration of response (DOR)

DOR will be assessed in the response evaluable analysis set (patients who are retreated with durvalumab in Cohort 2). To be consistent with RECIST 1.1 guidelines, the starting point for DOR is the first time at which the visit response is PR or CR.

DOR will be defined as the time from the date of first documented (which is subsequently confirmed) CR or PR until date of documented progression or death in the absence of disease progression (i.e. date of documented disease progression or death in the absence of disease progression, or censoring – date of first response + 1). DOR will be expressed in months.

The time of the initial response will be defined as the latest of the dates contributing towards the first visit that was CR or PR that was subsequently confirmed.

If a patient does not progress or die following a response, then their DOR analysis will be censored at the time of the latest date of assessment from their last evaluable RECIST assessment. However, if the patient progresses or dies immediately after two or more consecutive missed visits, the patient will be censored at the time of the latest evaluable RECIST 1.1 assessment prior to the two missed visits. The minimum elapsed time from the previous RECIST 1.1 assessment defined as two missed visits is calculated as $2 * (\text{the protocolled time between scans} + \text{the protocol allowed visit window})$: $2 * 12 = 24$ weeks. Note: NE visit is not considered as missed visit.

Same eCRF modules described in Section 3.1.1 will be used to retrieve the date of first documented CR or PR, the date of the latest evaluable RECIST 1.1 assessment, as well as the date of progression (if any). The date of death will be retrieved from “DEATH” module of the e-CRF.

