 - Dose per administration

- Dose units
- Action taken (dose not changed, drug interrupted, Drug permanently discontinued)
- Main reason for action taken (AE, other (to be specified))
- Treatment cycle delayed (y/n)
- Reason for treatment cycle delayed (Delayed hematological recovery, Adverse event, Disease symptoms, Logistic, Subject decision, Lab abnormality not reported as an AE, Other (to be specified))
- Concomitant and other treatments assessed under “Prior and Concomitant Medications (CM)” eCRF module. The following information will be collected:
 - Medication verbatim name
 - AE number for which medication taken
 - Medical history condition(s) number for which medication taken
 - Medication route of administration
 - Total daily dose
 - Dose unit
 - Medication dosing frequency
 - Treatment start date
 - Treatment stop date
 - Ongoing treatment (y/n)
 - Indication
- Concomitant Procedures assessed under “Concomitant Procedures (CONPRO)” eCRF module:
 - Procedure text
 - Procedure start date
 - Procedure reason
- Current and Concurrent cancer therapy assessed under “Current Cancer Therapy (CAPRX1)” and “Cancer Therapy - Post withdrawal of IP (CAPRX2)” eCRF modules respectively. The following information will be collected:
 - Cancer therapy agent name
 - Route of administration
 - Number of cycles
 - Therapy class (Immunotherapy, Hormonal Therapy, Cytotoxic chemotherapy, Systemic Therapy, Targeted Therapy, Antiangiogenic Therapy, Taxane chemotherapy, Radiopharmaceuticals, Platinum Chemotherapy, PARP Inhibitor, Biologic therapy, Experimental therapy, Other)

- Start and stop dates
- Best response (CR, PR, SD, Progression, Non-evaluable, Not applicable)
- Treatment status (line of therapy, adjuvant/non-adjuvant, palliative, maintenance, Definitive, Not applicable)
- Radiotherapy:
 - Timing against withdrawal of IP: previous, current, post
 - Radiotherapy site or region
 - Radiotherapy start and stop dates
 - Dose per fraction (Gy)
 - Number of fraction doses (total)
 - Treatment status (Adjuvant, Neo-adjuvant, Palliative, Definitive, Not applicable)

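### The SAP's ORR rule exempts all radiotherapy from the subsequent-therapy exclusion, so a confirmed response after post-durvalumab irradiation can count for durvalumab, which the protocol's rule does not allow

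*SAP*

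**What the plan says.** Protocol 9.3.3.3 sets the responder rule: "Patients who go off treatment without progression, receive a subsequent therapy, and then respond will not be included as responders in the ORR". It makes no exception for any type of therapy.

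SAP 3.1.1 repeats the exclusion and inserts a parenthesis: "note that for this analysis radiotherapy is not considered a subsequent anticancer therapy". It then spells out what the exclusion does when it is triggered: "both visits contributing to a response must be prior to subsequent therapy for the patient to be considered as a responder". On the assessment window it says: "Data obtained up until progression, or last evaluable assessment in the absence of progression, will be included in the assessment of ORR". A response must be "confirmed by repeat imaging not less than 4 weeks after the visit when the response was first observed", with no progression in between. SAP 5.2.2 uses every tumor assessment, scheduled or unscheduled.

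Protocol Table 7 (section 6.4) lists radiotherapy among the cancer treatments that may not be given during study treatment, with one exception: "Local treatment of isolated lesions, excluding target lesions, for palliative intent is acceptable". Protocol 7.1 leaves anticancer therapy after durvalumab to the Investigator's discretion, without limit.

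SAP section 7 states that the analyses have not changed from the protocol.

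**The concern.** The exemption sits in the sentence about patients who have already stopped durvalumab. During treatment it would matter little, because Table 7 restricts local treatment to palliative use and spares target lesions. Once durvalumab stops, that restriction lapses. Radiotherapy of any intent can then reach the lesions on which RECIST response is measured, and the SAP rule does not treat it as a reason to stop counting.

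ORR and DOR are the only stated measures of whether retreatment works. If shrinkage caused by radiotherapy enters ORR, the estimate no longer describes durvalumab alone. For ORR the error can only add responders. A reader who relies on SAP section 7 would also not learn that the SAP's rule is looser than the protocol's.

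**Working it through.** The plan gives no ORR assumption and no number of retreated patients, so there is no stated figure to reproduce. The check is a reading of the rules, followed by an illustration of size.

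**Step 1. Can the case arise under the rules?** Take a retreated Cohort 2 patient who stops durvalumab without progression and has not responded.

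- *Is irradiation of a target lesion possible?* Yes. Table 7's limit on radiotherapy applies while on study treatment, and protocol 7.1 sets none afterwards.
- *Does it trigger the SAP exclusion?* No. The parenthesis removes radiotherapy of every kind. Under protocol 9.3.3.3 nothing exempts it.
- *Are later scans inside the ORR window?* Under SAP 3.1.1 and 5.2.2, yes, until progression. Neither section cuts at durvalumab withdrawal or at radiotherapy.
- *Is the response confirmed?* It is if two PR or CR visits are at least 4 weeks apart with no progression between. Both may follow radiotherapy, or one may precede it and one follow.

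Such a patient can therefore be a responder under the SAP and, on the natural reading of subsequent therapy, a non-responder under the protocol.

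**Step 2. Do the scans exist?** Three places bear on this.

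- Protocol 8.2.3 describes the ORR and DOR assessments as collected at least every 12 weeks during treatment.
- Table 3 continues tumor assessment by local practice after treatment, but footnote j narrows it to the best response to the first therapy after durvalumab.
- The SAP's exclusion sentence concerns responses after discontinuation, so it presupposes that some later scans reach the response data.

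The route is open, but few patients are likely to take it.

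**Step 3. Size.** With x responders among n retreated patients, ORR = x/n. One added responder raises it by 1/n. The exact 95% interval is Clopper-Pearson: lower limit = Beta quantile at 0.025 with parameters (x, n − x + 1); upper limit = Beta quantile at 0.975 with parameters (x + 1, n − x). Both n and the 10% starting ORR are assumptions.

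| n (assumed) | ORR without the added patient | ORR with one added | Shift (1/n) |
|---|---|---|---|
| 10 | 1/10 = 10.0% (0.3 to 44.5) | 2/10 = 20.0% (2.5 to 55.6) | 10.0 points |
| 20 | 2/20 = 10.0% (1.2 to 31.7) | 3/20 = 15.0% (3.2 to 37.9) | 5.0 points |
| 40 | 4/40 = 10.0% (2.8 to 23.7) | 5/40 = 12.5% (4.2 to 26.8) | 2.5 points |
| 60 | 6/60 = 10.0% (3.8 to 20.5) | 7/60 = 11.7% (4.8 to 22.6) | 1.7 points |

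The shift lies well inside the interval at every n. It is a bias in the point estimate, not one that would change a test, since none is planned.

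**Step 4. Can the rule be narrowed with the data collected?** SAP section 4 lists, for radiotherapy, its timing relative to withdrawal of study drug, "Radiotherapy site or region", start and stop dates, and treatment status, which includes a palliative category. The protocol synopsis says only response outcomes go into the case report form, so matching an irradiated site to a particular target lesion may not always be possible.

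**The case against.** The strongest reply is that the case may never occur. The visit response is the Investigator's RECIST 1.1 assessment, and its rules are in protocol Appendix C, which is not in the supplied text. If Appendix C makes an irradiated target lesion not evaluable, the visit could not be read as PR. This stands as a real uncertainty, although SAP 3.1.1 does not invoke such a rule.

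The route is also narrow. Retreatment normally runs until progression, and ORR data stop there. The patient must stop early without progression, not already be a responder, be irradiated, and then respond with confirmation. Protocol 2.3.2.1 reports 5% to 10% stopping durvalumab for an adverse event in monotherapy studies. Among 20 patients that is 20 × 0.05 = 1 to 20 × 0.10 = 2, and only some of those would follow this route, though patients may stop for other reasons too. This also stands: one added responder in 20 is an illustration, not a forecast.

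The exemption probably has a sound purpose. Palliative radiotherapy to non-target lesions is permitted (Tables 7 and 8) and should not cost a patient a genuine response. A reader might infer that the parenthesis should simply be deleted. The documents do not support that: because both response visits must precede subsequent therapy, deletion could disqualify a true responder who had such palliative treatment between first response and confirmation.

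Finally, ORR is secondary and descriptive, falls back on listings if numbers are too small, and protocol 9.3.2 defers detail to the SAP, which states the exemption openly. That lowers the stakes. It does not explain why the exemption is unlimited or why section 7 reports no change.

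**Conclusion.** The point holds as a mismatch between the SAP and protocol responder rules, with a possible but probably small upward bias in ORR. Each affected patient adds 1/n: 5 points at an assumed n of 20, and 1.7 to 10 points over assumed n of 60 down to 10. This rests on post-durvalumab scans reaching the RECIST data and on Appendix C not making irradiated lesions not evaluable. Neither can be settled from the supplied text. The primary safety objective is unaffected.

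Three stronger readings are not supported:

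- *Any patient irradiated after durvalumab whose tumor shrinks becomes a responder.* The response must be a confirmed PR or CR without earlier progression and must be recorded in the RECIST modules.
- *The bias also favours durvalumab in TTR and DOR.* A response first seen after irradiation is a late one and would tend to lengthen TTR among responders. Its effect on median DOR could go either way.
- *DOR is wrong because it has no cut at later therapy.* SAP 3.1.2 runs DOR "until date of documented progression or death in the absence of disease progression", which matches protocol 9.3.3.4. Following response through later therapy is a legitimate choice of estimand.

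**What to change.** In SAP 3.1.1, limit the exemption to palliative radiotherapy to non-target lesions, the kind Table 7 permits on treatment. Count any other radiotherapy after durvalumab withdrawal as subsequent therapy, so that only assessments before it contribute to ORR and to the first-response date used for TTR.

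Apply this with the eCRF fields for timing against study drug withdrawal, site, dates and treatment status. Where the recorded site cannot be matched to target or non-target lesions, count post-withdrawal radiotherapy as subsequent therapy. State the remaining difference from protocol 9.3.3.3 in SAP section 7.

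A DOR analysis censored at subsequent therapy is at most an optional sensitivity analysis.

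The cost is a few sentences of SAP text and a little programming, with no new data. The downside is that ORR may look slightly less favourable, and the default for unmatched sites could occasionally remove a genuine responder.

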3.1.2 Duration of response (DOR)

DOR will be assessed in the response evaluable analysis set (patients who are retreated with durvalumab in Cohort 2). To be consistent with RECIST 1.1 guidelines, the starting point for DOR is the first time at which the visit response is PR or CR.

DOR will be defined as the time from the date of first documented (which is subsequently confirmed) CR or PR until date of documented progression or death in the absence of disease progression (i.e. date of documented disease progression or death in the absence of disease progression, or censoring – date of first response + 1). DOR will be expressed in months.

The time of the initial response will be defined as the latest of the dates contributing towards the first visit that was CR or PR that was subsequently confirmed.

If a patient does not progress or die following a response, then their DOR analysis will be censored at the time of the latest date of assessment from their last evaluable RECIST assessment. However, if the patient progresses or dies immediately after two or more consecutive missed visits, the patient will be censored at the time of the latest evaluable RECIST 1.1 assessment prior to the two missed visits. The minimum elapsed time from the previous RECIST 1.1 assessment defined as two missed visits is calculated as $2 * (\text{the protocolled time between scans} + \text{the protocol allowed visit window})$: $2 * 12 = 24$ weeks. Note: NE visit is not considered as missed visit.

Same eCRF modules described in Section 3.1.1 will be used to retrieve the date of first documented CR or PR, the date of the latest evaluable RECIST 1.1 assessment, as well as the date of progression (if any). The date of death will be retrieved from “DEATH” module of the e-CRF.

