Cohort 2 includes patients who completed durvalumab monotherapy or in combination with any other approved or investigational anticancer agents in a parent study, without confirmed PD during the period of treatment, and who are potentially eligible for retreatment with durvalumab. The patient should not have received any other approved or investigational anticancer agents since completion of durvalumab treatment. Patients who completed the prespecified duration of treatment with durvalumab in a parent clinical study, who received clinical benefit and then subsequently experienced confirmed PD after completion of planned treatment, will be permitted to restart durvalumab treatment provided they meet the eligibility criteria. If a patient was already retreated with durvalumab in the parent clinical study and retreatment has ended, they are no longer eligible for retreatment in this study. In addition, intervening chemotherapy treatment will not be allowed before retreatment with durvalumab. Cohort 2 patients who will be eligible for future retreatment with durvalumab must agree to reconsenting to start retreatment and meet the eligibility criteria detailed in Sections 5.1 and 5.2. Patients who undergo retreatment will follow assessments as per the SoA for Cohort 1 until confirmed PD, unless unacceptable toxicity, withdrawal of consent, or another discontinuation criterion is met (Table 2). Only 1 course of retreatment is allowed (inclusive of any retreatment in the parent

clinical study). Treatment beyond disease progression is allowed at the Investigator's discretion, if it is in the patient's best interest. The baseline imaging results for Cohort 2 must be available within 28 days of retreatment. While on retreatment, follow-up tumor assessments will be performed according to the Investigator's standard practice (at least every 12 weeks) using RECIST v1.1 (Table 1). Upon discontinuation of durvalumab, patients may receive any subsequent anticancer therapy at the discretion of the Investigator and will follow the SoA detailed for Cohort 3 for safety and survival follow-up (Table 3).

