Clinical chemistry ^h		X	X	X		X	X	X	X	X
Hematology ^h		X	X	X		X	X	X	X	X
TSH (reflex free T3 or free T4) ⁱ		X	X	X		X	X	X	X	X
Pregnancy test ^j		X				X	X	X	X	X

	Follow-up before retreatment				Retreatment					
	Time since the last dose of study drug ^a			Long-term follow-up	Baseline ^b / C1	C2	C3	C4	C5 onwards ^c	
Week	Baseline/ Enrollment ^a	Day (±3 days)	Day (±7 days)		Every 3 months (±2 weeks)	0	Q4W ±3 days unless dosing needs to be held for toxicity reasons			
Day		30	60	90		1	Q28days ±3 days unless dosing needs to be held for toxicity reasons			
Monitoring										
AE/SAE assessment ^k		X	X	X		Throughout				
Survival status ^l					X					
Study drug administration										
Durvalumab (monotherapy) ^m						X	X	X	X	
Tumor assessment										
Tumor assessment ⁿ	Assessment performed according to the Investigator’s standard practice until withdrawal of consent, progression or death.					X ^o	Assessment performed according to RECIST v1.1 as determined by the Investigator (at least every 12 weeks) until withdrawal of consent, progression or death.			

- a. Follow-up visits are performed based on the duration since the last dose of study drug in either the parent clinical study or current study (whichever most recently administered the study drug). Patients who are more than 90 days beyond the last dose of study drug, will not undergo follow-up for AEs/SAEs, vital signs, concomitant medications, or laboratory safety assessments; these patients will be followed for survival and undergo tumor assessment per Investigator’s standard practice.
- b. Baseline assessments may be performed over more than 1 visit if necessary. If laboratory or imaging procedures were performed for alternate reasons prior to signing the consent, these can be used for baseline assessment purposes with consent of the patient. However, all baseline laboratory assessments must be obtained within 3 days prior to Day 1 (first retreatment visit), and baseline imaging results must be obtained within 28 days prior to Day 1 of retreatment. Baseline laboratory assessments performed within 3 days prior to Day 1 do not need to be repeated at Day 1. Patients with documented HIV test results from the parent clinical study do not need to undergo a repeat test, but HBV and HCV must be retested within the 28-day period.

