8. STUDY ASSESSMENTS AND PROCEDURES

Data collection and frequency are summarized by each of the 3 cohorts below:

In Cohort 1, all durvalumab treatment cycle assessments will occur every 4 weeks until confirmed PD, unless unacceptable toxicity, withdrawal of consent, or another discontinuation criterion is met. The most recent imaging results from the parent clinical study may be used for baseline tumor assessments, provided it was obtained within 28 days prior to Day 1, Cycle 1. Tumor assessments throughout all cycles will be performed according to RECIST v1.1, as determined by the Investigator (at least every 12 weeks) until withdrawal of consent, progression, or death. The patients will continue their durvalumab treatment and all cycle assessments every 4 weeks ± 3 days unless dosing needs to be held for toxicity reasons ([Table 1](#)).

Cohort 2 follow-up prior to retreatment with durvalumab monotherapy follows the SoA for Cohort 3, while patients who undergo retreatment begin the assessment as per the SoA for patients in Cohort 1. During the follow-up of patients before retreatment, they will undergo assessments for vital signs, concomitant medications, laboratory safety and AE/SAE at 30 days (± 3 days), 60 days (± 7 days), and 90 days (± 7 days) since the last dose of study drug. The assessment for concomitant medications will be collected throughout 90 days post durvalumab discontinuation. The survival status for these patients will be collected every 3 months (± 2 weeks) beginning 90 days after the last dose of the study drug and tumor assessments will be performed according to the Investigator's standard practice until withdrawal of consent, progression, or death. For those that start retreatment, patients will continue their durvalumab monotherapy and all cycle assessments every 4 weeks ± 3 days unless dosing needs to be held for toxicity reasons. While on retreatment, tumor assessments and disease progression will be determined by the Investigator following RECIST v1.1 ([Table 2](#)).

Cohort 3 includes safety and survival follow-up only for patients previously treated with durvalumab monotherapy or durvalumab in combination with any other approved or investigational anticancer agents who are no longer receiving durvalumab and are not eligible to receive retreatment. The patients would undergo assessments as per the SoA (Table 3).

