8.2.3 Clinical endpoint assessments

Data for the following endpoints will be collected and may be evaluated as part of the analysis in the parent clinical studies from which the patients originated. Survival data will be collected in terms of OS in all patients. Efficacy variables will be collected in terms of ORR and DOR for patients in Cohort 2 who start retreatment according to clinical practice (so long as they satisfy eligibility criteria in Section 5.1). These endpoints are defined below:

- OS is defined as the time from date of randomization/enrollment in the parent clinical study until the date of death by any cause (all cohorts).
- ORR is defined as the number (%) of patients with a confirmed response of complete response (CR) or partial response (PR) from the re-initiation of treatment with durvalumab monotherapy (Cohort 2).
- DOR is defined as the time from first documented CR or PR until the time of first documented disease progression or death in the absence of disease progression (Cohort 2).

Tumor assessments, performed by the Investigator according to standard practice, to determine ORR and DOR will be collected for patients in Cohorts 1 and 2 at least every 12 weeks while the patient is receiving treatment. Assessments should be performed as deemed medically appropriate by the Investigator, for the purpose of maintaining the safety and wellbeing of the patient. Investigator reported response will be collected and summarized.

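### The 24-week limit for two missed visits in the DOR censoring rule leaves out the window named in its own formula, so on a 12-week schedule one missed scan can be enough to censor a progression

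*SAP*

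**What the plan says.** SAP Section 3.1.2 states the rule in words: "if the patient progresses or dies immediately after two or more consecutive missed visits, the patient will be censored", the censoring date being the last evaluable RECIST 1.1 assessment before the missed visits. It then gives an operational limit: "The minimum elapsed time from the previous RECIST 1.1 assessment defined as two missed visits is calculated as" two times the sum of the protocolled scan interval and the protocol-allowed visit window, evaluated as 2 x 12 = 24 weeks. No value is given for the window, and the SAP does not say that it is zero.

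The protocol sets the scan frequency for retreated Cohort 2 patients in Section 1: "While on retreatment, follow-up tumor assessments will be performed according to the Investigator's standard practice (at least every 12 weeks) using RECIST v1.1". The tumor assessment row of Table 2 says the same: "Assessment performed according to RECIST v1.1 as determined by the Investigator (at least every 12 weeks) until withdrawal of consent, progression or death". Neither place gives a tolerance in days. The on-treatment tolerance that the protocol does state is for the 4-weekly cycle visits (Section 8): "patients will continue their durvalumab monotherapy and all cycle assessments every 4 weeks ± 3 days unless dosing needs to be held for toxicity reasons". It is not said to apply to scans.

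SAP Section 5.2.3 plans Kaplan-Meier plots, a median with 95% CI and swimmer plots. It plans no DOR analysis without the missed-visit rule. Protocol Section 9.3.3.4 defines DOR with no missed-visit censoring.

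**The concern.** The formula and the number do not match unless the window is zero. A window term allows for ordinary variation in scan dates, so that a gap created by one missed scan is not taken for a gap created by two. Without it, the limit sits exactly where the scan after one missed visit is due on a 12-week schedule. That scan then falls on or over the limit about as often as under it.

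The written rule requires two missed visits, whereas the number can be met after one. A programmer who follows the words and one who follows the number would get different event counts from the same data. The responder set in retreated Cohort 2 may be small, so a few progressions reclassified as censored would show in the event count.

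**Working it through.** **Inputs.** Scan interval: 12 weeks = 84 days, the longest interval the protocol allows on retreatment. Limit: 2 x (interval + window), from SAP 3.1.2. Scan window: none found in the supplied text, so a range is used.

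**Step 1. Reproduce the SAP figure.** 2 x (12 + 0) = 24 weeks = 168 days. It is reproduced only with a zero window. Other values give:

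| Assumed window | Limit |
|---|---|
| 3 days (the cycle-visit tolerance) | 2 x (84 + 3) = 174 days = 24.86 weeks |
| 1 week | 2 x (84 + 7) = 182 days = 26 weeks |
| 2 weeks | 2 x (84 + 14) = 196 days = 28 weeks |

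**Step 2. Compare the limit with the gaps that missed scans create.** If progression is found at the first attended scan after the missed ones, the gap is 2 x interval after one missed scan and 3 x interval after two.

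| Interval (weeks) | Gap after one missed (weeks) | Gap after two missed (weeks) | Effect of a 24-week (>=) limit |
|---|---|---|---|
| 6 | 12 | 18 | neither censored |
| 8 | 16 | 24 | only two missed censored |
| 9 | 18 | 27 | only two missed censored |
| 12 | 24 | 36 | both censored |

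The fault appears at the 12-week interval, which is the one the SAP uses.

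**Step 3. How often one missed scan reaches the limit.** Let both scan dates vary independently and uniformly over whole days within w days of schedule (assumption). The gap is 168 + (e2 - e1) days, where e1 and e2 are the deviations of the two scans.

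- w = 3: 7 x 7 = 49 pairs. The gap exceeds 168 days in 21 (43%) and is at least 168 in 28 (57%).
- w = 7: 15 x 15 = 225 pairs. The gap exceeds 168 days in 105 (47%) and is at least 168 in 120 (53%).
- With the same window in the formula, one pair reaches the limit: 1/49 = 2.0% at 174 days and 1/225 = 0.4% at 182 days. Read strictly (>), none does.
- Progressions after two missed scans (about 252 days) are all still caught.

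**Step 4. One patient.** The last evaluable scan is 84 days after first response, the next scan is missed, and progression is found 252 days after response. The gap is 252 - 84 = 168 days. Under >=, DOR is censored at 84 + 1 = 85 days (2.8 months) rather than being an event at 252 + 1 = 253 days (8.3 months). If the last scan is one day late, this happens under either reading.

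**Step 5. Effect on the analysis.** Simulation with 200,000 responders, exponential time to progression with median 274 days, scans every 84 days give or take 7, scans missed at random, strict reading (all assumptions):

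| Scans missed | Progressions censored, 24-week limit | Progressions censored, 26-week limit |
|---|---|---|
| 10% | 9.6% | 2.4% |
| 20% | 20.4% | 8.7% |

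The two limits give median DORs that differ by 1 to 3 days.

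**The case against.** The strongest reply is that 24 weeks is no mistake. The protocol asks for scans at least every 12 weeks, so 12 weeks is a maximum and a later scan is simply late. With no allowed window, 2 x 12 is correct. Protocol Section 8.2 refers to Appendix C for protocol-specific tumor assessment requirements. That appendix is not in the text available here, so a window there, or a deliberate zero, cannot be ruled out. This stands as a limit on what can be said about intent. It does not remove the conflict: even with an intended zero, an on-time (under >=) or late scan after one missed visit meets a limit meant for two.

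Deaths behave differently, and this stands. On a 12-week schedule, a death more than 24 weeks after the last scan does follow two missed scans, so for deaths the zero-window limit is right.

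A reader might infer more than the documents support:

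- **That every progression after one missed scan is censored.** One found before 24 weeks, at an early or unscheduled scan, remains an event. At shorter intervals the problem lessens or disappears, and at 6 weeks the limit is too lenient.
- **That the rule makes DOR look longer.** Progression happened somewhere between the two scans. Dating it at the later scan also lengthens DOR, and censoring at the last evaluable scan is a recognised way to avoid that. The documents say nothing about why scans would be missed.
- **That it is worse after retreatment stops.** Scans are required "will be collected for patients in Cohorts 1 and 2 at least every 12 weeks while the patient is receiving treatment"; afterwards they follow standard practice. No interval is stated for that period, so the effect cannot be sized. Retreatment normally runs until confirmed progression, so many DOR events would fall within the 12-week schedule.

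**Conclusion.** The point holds for patients scanned every 12 weeks. The 24-week limit equals the SAP's formula only with a zero window, and it lets one missed scan trigger a rule written for two or more. About 43% to 57% of progressions found at the scan after a single missed visit are affected. The range covers assumed deviations of 3 to 7 days and both readings of the limit. These percentages apply to that subgroup, not to all responders; the overall share depends on a missed-scan rate that the documents do not give.

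The consequence is modest. The number of DOR events changes, the median barely does, and the direction of any bias is not established. DOR is a secondary, descriptive endpoint with no hypothesis test, and only listings will be used to assess it if too few patients are retreated. This is a worthwhile correction to the SAP, not a threat to the study's conclusions.

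**What to change.** In SAP Section 3.1.2:

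1. Set a scan window for analysis and put it in the formula. With 1 week the limit is 2 x (12 + 1) = 26 weeks, still well below the roughly 36 weeks at which a progression after two missed 12-weekly scans is found. The SAP should call it an analysis window, since the supplied protocol text gives none for scans.
2. State whether the limit is > or >=.
3. Add a sensitivity analysis of DOR that counts all progressions and deaths as events regardless of missed visits, so the reader can see how many events the rule removes.

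The cost is a short SAP edit and one more analysis. There are two trade-offs. A few deaths between 24 and 26 weeks after the last scan would become events although two scans were missed. For patients scanned every 8 weeks, two missed scans give a nominal gap of 24 weeks, which a 26-week limit would no longer catch. The sensitivity analysis shows how far the results depend on the rule.
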